8.4 Stable Disease Duration

Stable disease duration will be measured from the time of start of treatment until the criteria for progression are met, taking as reference the smallest sum on study (including baseline).

8.5 Methods of Measurement

The same method of assessment and the same technique should be used to characterize each identified and reported lesion at baseline and during follow-up. Assessments should be identified on a calendar schedule and should not be affected by delays in therapy. While on study, all lesions recorded at baseline should have their actual measurements recorded at each subsequent evaluation, even when very small (e.g. 2 mm). If it is the opinion of the radiologist that the lesion has likely disappeared, the measurement should be recorded as 0 mm. If the lesion is believed to be present and is faintly seen but too small to measure, a default value of 5 mm should be assigned. For lesions which fragment/split add together the longest diameters of the fragmented portions; for lesions which coalesce, measure the maximal longest diameter for the “merged lesion”.

8.5.1 Clinical Lesions. Clinical lesions will only be considered measurable when they are superficial and  $\geq 10\text{mm}$  as assessed using calipers (e.g. skin nodules). For the case of skin lesions, documentation by colour photography including a ruler to estimate the size of the lesion is recommended. If feasible, imaging is preferred.

8.5.2 Chest X-ray. Chest CT is preferred over chest X-ray, particularly when progression is an important endpoint, since CT is more sensitive than X-ray, particularly in identifying new lesions. However, lesions  $\geq 20\text{ mm}$  on chest X-ray may be considered measurable if they are clearly defined and surrounded by aerated lung.

8.5.3 CT, MRI. CT is the best currently available and reproducible method to measure lesions selected for response assessment in the body while MRI is best modality for the CNS. This guideline has defined measurability of lesions on CT or MRI scan based on the assumption that slice thickness is 5 mm or less. When scans have slice thickness greater than 5 mm, the minimum size for a measurable lesion should be twice the slice thickness. Other specialized imaging or other techniques may also be appropriate for individual case [ref RECIST 1.1]. For example, while PET scans are not considered adequate to measure lesions, PET-CT scans may be used providing that the measures are obtained from the CT scan and the CT scan is of identical diagnostic quality to a diagnostic CT (with IV and oral contrast).

8.5.4 Ultrasound. Ultrasound is not useful in assessment of lesion size and should not be used as a method of measurement. If new lesions are identified by ultrasound in the course of the study, confirmation by CT is advised.

8.5.5 Endoscopy, Laparoscopy. The utilization of these techniques for objective tumour evaluation is not advised. However, they can be useful to confirm complete pathological response when biopsies are obtained or to determine relapse in trials where recurrence following complete response or surgical resection is an endpoint.

8.5.6 Cytology, Histology. These techniques can be used to differentiate between PR and CR in rare cases if required by protocol (for example, residual lesions in tumour types such as germ cell tumours, where known residual benign tumours can remain). When effusions are known to be a potential adverse effect of treatment (e.g. with certain taxane compounds or angiogenesis inhibitors), the cytological confirmation of the neoplastic origin of any effusion that appears or worsens during treatment when the measurable tumour has met criteria for response or stable disease is advised to differentiate between response or stable disease and progressive disease.

## 9.0 SERIOUS ADVERSE EVENT REPORTING

This protocol does not contain investigational agent(s), and adverse events occurring as a result of this commercially available treatment should be reported to CCTG in the manner described below. In addition, your local Research Ethics Board (REB) should be notified.

The descriptions and grading scales found in the NCI Common Terminology Criteria for Adverse Events (CTCAE) will be utilized for Adverse Event (AE) reporting (version can be found in Appendix V). All appropriate treatment areas should have access to a copy of the CTCAE. A copy of the CTCAE can be downloaded from the CTEP web site:

[http://ctep.cancer.gov/protocolDevelopment/electronic\\_applications/ctc.htm](http://ctep.cancer.gov/protocolDevelopment/electronic_applications/ctc.htm).

All serious adverse events (SAE) defined as per ICH guidelines (see below) and other adverse events must be recorded on case report forms. In addition, all “reportable” serious adverse events are subject to expedited reporting using the CCTG SAE form. The term ‘reportable SAE’ is used in the definitions which follow to describe those SAEs which are subject to expedited reporting to CCTG.

### 9.1 Definition of a Reportable Serious Adverse Event

- All serious adverse events which are unexpected and related to protocol treatment must be reported in an expedited manner (see Section 9.2 for reporting instructions). These include events occurring during the treatment period (until 30 days after last protocol treatment administration) and at any time afterwards.
- Unexpected adverse events are those which are not consistent in either nature or severity with information contained in the investigator brochure or product monograph.
- Adverse events considered related to protocol treatment are those for which a relationship to the protocol agent cannot reasonably be ruled out.
- A serious adverse event (SAE) is any adverse event that at any dose:
  - results in death
  - is life-threatening
  - requires inpatient hospitalization or prolongation of existing hospitalization (excluding hospital admissions for study drug administration, transfusional support, scheduled elective surgery and admissions for palliative or terminal care)
  - results in persistent or significant disability or incapacity
  - is a congenital anomaly/birth defect
- Any new primary cancers and treatment emergent malignancies (including squamous cell carcinoma and new primary melanoma) with the exception of basal cell carcinoma (BCC). BCC should be reported as an AE or SAE based on the discretion of the investigator.
- Symptomatic LVEF decrease that meets stopping criteria or asymptomatic LVEF decrease that does not recover, as outlined as LVEF guidance (Section 7.1.3 Table 2)
- Retinal pigment epithelial detachment (RPED) or retinal vein occlusion (RVO)

Medical and scientific judgment should be exercised in deciding whether expedited reporting is appropriate in other situations such as important medical events that may not be immediately life-threatening or result in death or hospitalization but may jeopardize the patient or may require intervention to prevent one of the events listed above.

## 9.2 Serious Adverse Event Reporting Instructions

All reportable serious adverse events must be reported using a web-based Electronic Data Capture (EDC) system being used for this trial. For details about accessing the EDC system and completing the on-line SAE report form, please refer to the CCTG Generic Data Management Guidebook for EDC Studies posted on the IND.224 section of the CCTG website ([www.ctg.queensu.ca](http://www.ctg.queensu.ca)).

Within 24 hours:      Complete preliminary Serious Adverse Event Report and submit to CCTG via EDC system.

Within 7 days:      Update Serious Adverse Event Report as much as possible and submit report to CCTG via EDC system.

*EDC SAE web application interruption:*

In the rare event that internet connectivity to the EDC SAE system is disrupted, please print and complete a paper copy of the SAE Report, available from the trial specific website.

FAX paper SAE Report to:

IND.224 Study Coordinator  
Canadian Cancer Trials Group  
[contact]

Please use the same timelines for submission as for direct EDC reporting.

Once internet connectivity is restored, the information that was FAXED to CCTG on the paper SAE Report must also be entered by the site into the EDC SAE web application.

*Local internet interruption:*

If you are unable to access the EDC SAE system, and cannot access a paper copy of the SAE Report from the trial website, please phone the IND.224 trial team [contact]) to obtain a copy of the SAE Report by FAX. Once completed, the report must be FAXED back to CCTG as indicated above. Once internet connectivity is restored, the information that was FAXED to CCTG on the paper SAE Report must also be entered by the site into the EDC SAE web application.

In cases of prolonged internet interruptions, please contact the CCTG Safety Desk for further instructions [contact]).

## 9.3 Other Protocol Reportable Events – Exposure Reporting, and Pregnancy Reporting

### 9.3.1 Pregnancy Prevention

Women of childbearing potential (WOCBP) and males who are enrolled in the trial must have agreed to use contraceptive method(s) as described in Eligibility Criteria 4.2.13. Investigators may wish to additionally advise the female partners of male participants about pregnancy prevention guidelines when appropriate and compliant with local policy.

### 9.3.2 Pregnancy Reporting

The investigator is required to report to CCTG any pregnancy occurring in female participants, and female partners of male participants. Pregnancies occurring up to 4 months after the completion of study treatment must also be reported.

The investigator should report the pregnancy in a timely manner, within 24 hours of learning of the pregnancy using the CCTG Pregnancy Reporting Form available from the trial webpage.

Once informed consent has been obtained, the form should be updated to provide further pregnancy information and to reflect the outcome of the pregnancy. All follow-up reports must be submitted to CCTG in a timely manner. For pregnant partner of trial participant (and pregnant participants, if required by local policy), a copy of the signed signature page of the pregnancy follow-up consent must be submitted to CCTG.

Documents outlined above (including updates) must be sent to the CCTG safety desk [contact]/ [[contact]](mailto:[contact])).

If the pregnancy results in death; is life-threatening; requires inpatient hospitalization or prolongation of existing hospitalization; results in persistent or significant disability/incapacity; is a congenital anomaly/birth defect, then an SAE report must be additionally submitted as described above. Please note, hospitalization for labour/delivery alone does not constitute an 'inpatient hospitalization' for the purposes of pregnancy reporting.

### 9.3.3 Exposure Reporting (Non-study Participants)

The investigator is required to report to CCTG any incidence of exposure to study agent(s). Exposure is defined as significant, direct, contact/inhalation/consumption of agent(s) by non-study participant (an individual who is not otherwise participating in this clinical trial). An example of an exposure includes a non-study participant swallowing study medication. The investigator is responsible for determining significance, based on the agent to which the individual is exposed.

The investigator should report the exposure in a timely manner, within 24 hours of learning of the exposure, using the CCTG Exposure Reporting Form available from the trial webpage.

Once informed consent has been obtained, the form should be updated to provide further exposure information and to reflect the outcome of the exposure as the information becomes available upon appropriate follow-up of the exposed individual. All follow-up reports must be submitted to CCTG in a timely manner. A copy of the signed exposure follow-up consent signature page must also be submitted to CCTG.

Documents outlined above (including updates) must be sent to the CCTG safety desk [contact]/ [[contact]](mailto:[contact])).

If the exposure results in death; is life-threatening; requires inpatient hospitalization or prolongation of existing hospitalization; results in persistent or significant disability/incapacity; is a congenital anomaly/birth defect, then an SAE report must be additionally submitted as described above.

9.4 CCTG Responsibility for Reporting Serious Adverse Events to Health Canada

The CCTG will provide expedited reports of SAEs to Health Canada for those events which meet regulatory requirements for expedited reporting, i.e. events which are BOTH serious AND unexpected, AND which are thought to be related to protocol treatment (or for which a causal relationship with protocol treatment cannot be ruled out).

9.5 CCTG Reporting Responsibility to Novartis

Novartis will be notified of all protocol reportable serious adverse events within 1 working day.

9.6 Novartis Reporting Responsibilities

Novartis will report all regulatory reportable serious adverse events from non-CCTG trials (Safety Updates) to Health Canada and also provide to CCTG within the timelines outlined in the contract. CCTG will review these events to determine which meet the criteria (serious, unexpected, drug related) for IND.224 investigator distribution.

9.7 Reporting Safety Reports to Investigators

CCTG will notify Investigators of all Safety Reports (Serious Adverse Events (SAEs) from this trial and Safety Updates (SUs) from other clinical trials) that are reportable to regulatory authorities in Canada as reported to the CCTG. This includes all serious events that are unexpected and related (i.e. possibly, probably, or definitely) to protocol treatment. The reports will be posted to the CCTG trial IND.224 web-based safety monitoring utility.

Investigators must notify their Research Ethics Boards (REBs) of events which involve corrective action(s) to be taken as a result of the event(s) such as protocol and/or informed consent changes. The date of REB Submission for these SAEs and SUs will need to be entered into the CCTG trial IND.224 web based safety monitoring utility and documentation of REB submission must be retained in the study binder on site. The REB submission template provided by CCTG can be used to assist with tracking, submission, filing and monitoring.

The submission of events to your ethics board should be done as soon as possible (we suggest within 30 days). REB submissions greater than 90 days from the date of notification will be regarded as delinquent and a major deficiency will be assigned. These safety reports are to be filed in the trial files on site.

10.0 PROTOCOL TREATMENT DISCONTINUATION AND THERAPY AFTER STOPPING

10.1 Criteria for Discontinuing Protocol Treatment

Patients may stop protocol treatment in the following instances:

- Intercurrent illness which would, in the judgement of the investigator, affect assessments of clinical status to a significant degree, and require discontinuation of protocol therapy.
- Unacceptable toxicity as defined in Section 7.0.
- Tumour progression or disease recurrence as defined in Section 8.0.
- Request by the patient.
- Efforts should be made to maintain the investigations schedule and continue follow-up, even if patients discontinue protocol treatment prematurely and/or no longer attend the participating institution.

10.2 Therapy After Protocol Treatment is Stopped

At the discretion of the investigator.

Note, patients with CNS progression that can be managed with additional SRS or whole brain radiotherapy can continue on dabrafenib and trametinib if there is no evidence of progression outside of the CNS and it is felt that continuation of systemic treatment may benefit the patient.

10.3 Follow-up Off Protocol Treatment

All patients will be seen at 4 weeks after completion of protocol therapy. Thereafter, continued follow-up is not required for patients who go off protocol treatment with progressive disease, except to document ongoing toxicities (until resolved to  $\leq$  grade 2) and late toxicities (including second malignancies). For patients who go off protocol treatment with CR, PR, or SD ongoing, follow-up will be required every 3 months until relapse. Final report (Death Report) will be required on all patients. Due within 2 weeks of knowledge of death (see Appendix III - Documentation for Study).

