### 6.2 Registration

Registration will be provided electronically.

*Note:* The validity of results of the trial depends on the authenticity of and the follow-up of all patients entered into the trial. Under no circumstances, therefore, may an allocated patient's data be withdrawn prior to final analysis, unless the participant withdraws from the trial and requests that data collection/submission cease from the point in time of withdrawal.

All eligible patients admitted to the trial will be followed by the coordinating centre. It is the responsibility of the physician in charge to satisfy himself or herself that the patient is indeed eligible before requesting registration/randomization.

All registered patients are to be followed until death or until sites are informed by CCTG that further follow-up is no longer required. The follow-up requirements for ineligible patients who have received no protocol therapy include submission of the Baseline Report. Data submission for ineligible participants who have received at least one dose of protocol therapy should be followed according to the protocol to allow for treatment and adverse event assessment.

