APPENDIX III - DOCUMENTATION FOR STUDY

Follow-up is required for patients from the time of registration and will apply to all eligible and ineligible patients. This trial will use a web-based Electronic Data Capture (EDC) system for all data collection including SAE reporting (see Section 9.0 for details regarding SAE reporting). For details about accessing the EDC system and completing the on-line Case Report Forms, please refer to the Data Management Guidebook posted on the IND 224 area of the CCTG web-site ([www.ctg.queensu.ca](http://www.ctg.queensu.ca)).

Electronic Case Report Form	To be Completed/Submitted Electronically	Supporting Documentation to be sent using Supporting Document Upload Tool*
PATIENT ENROLLMENT FOLDER	Must be completed at time of registration to confirm eligibility.	
BASELINE REPORT	Due within 2 weeks of patient registration.	Copies of signature pages of main consent forms; relevant pathology & radiology reports; LVEF report
TREATMENT REPORT	To be completed every 4 weeks (i.e. after each cycle/reporting period). Due within 2 weeks of end of cycle/reporting period. This form documents treatment, adverse events, investigations and response assessment for each cycle/reporting period.	Relevant radiology reports; LVEF report (if applicable)
END OF TREATMENT REPORT	To be completed when patient permanently discontinues protocol treatment. Due within 2 weeks of end of protocol treatment.	
4 WEEK POST TREATMENT REPORT	To be completed once on all patients, 4 weeks after the end of the last cycle. Due within 2 weeks after contact with patient.	
FOLLOW-UP REPORT	Continued follow-up is not required for patients who go off protocol treatment with progressive disease , except to document ongoing toxicities (until resolved to $\leq$ grade 2) and late toxicities (including second malignancies). For patients who go off protocol treatment with response or stable disease ongoing , Follow-Up form to be completed every 3 months until relapse/progression. Due within 2 weeks after contact with patient.	Relevant radiology reports.
RELAPSE/PROGRESSION REPORT	To be completed at the time of disease relapse or progression. Due within 2 weeks after contact with patient.	Relevant radiology reports.
DEATH REPORT **	Death Report will be required on all patients. Due within 2 weeks of knowledge of death.	Autopsy report, if done.

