SERIOUS ADVERSE EVENT REPORT FORM	All reportable serious adverse events must be reported as described in Section 9.0. Preliminary CCTG Serious Adverse Event Report due within 24 hours. Updated CCTG Serious Adverse Event Report due within 7 days .	All relevant test reports, admission, discharge summaries/notes.

\* Supporting documents should be uploaded immediately after the report they refer to has been submitted electronically.

\*\* NB It is the investigator's responsibility to investigate and report the date/cause of death of any patient who dies during this period. Any death that occurs during this protocol therapy or within 30 days after last dose must also be reported as a Serious Adverse Event as described in section 9.

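### Section 6.2 follows every patient to death or release, but 10.3, Appendix III and the flowsheet stop routine contact after progression, so overall survival has no planned source of last-alive dates

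*Combined protocol and SAP*

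**What the plan says.** Overall survival is a secondary objective (Sections 1.2 and 12.1). Neither Section 8 nor Section 12 gives it a time origin, a censoring rule or a data cut-off.

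Section 6.2 sets a general rule: "All registered patients are to be followed until death or until sites are informed by CCTG that further follow-up is no longer required".

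Section 10.3 sets the working schedule:
- "All patients will be seen at 4 weeks after completion of protocol therapy".
- After that visit, "continued follow-up is not required for patients who go off protocol treatment with progressive disease". The exceptions are ongoing toxicities until they settle to grade 2 or less, and late toxicities including second malignancies.
- For patients who stop with CR, PR or SD, "follow-up will be required every 3 months until relapse".
- A Death Report is needed for every patient: "Due within 2 weeks of knowledge of death".

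The Follow-up Report row of Appendix III repeats 10.3. The Section 5.0 flowsheet limits its 3-month column to patients without confirmed PD and those with ongoing toxicities. Appendix III also opens with a general statement: "Follow-up is required for patients from the time of registration and will apply to all eligible and ineligible patients". It adds in the form table that a "Death Report will be required on all patients", and in a note that "It is the investigator's responsibility to investigate and report the date/cause of death of any patient who dies during this period".

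**The concern.** The general rule and the working schedule disagree about patients whose disease has progressed. Sites work from the schedule and the form table. A site that follows them reports deaths it hears of but supplies no later date for patients who are still alive. The gap also covers patients who stop in response or with stable disease and later relapse, because their 3-monthly follow-up ends at relapse.

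A Kaplan-Meier estimate needs deaths and survivors to be observed over the same period. Two opposite errors are possible:
- If nearly all deaths are reported but survivors are censored at last scheduled contact, survivors leave the risk set early while patients who will die stay in it. The curve is then too low.
- If many later deaths are never learned of, those patients are censored alive and the curve is too high.

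The direction depends on unplanned reporting, and the confidence interval does not reflect it. The trial is single-arm, so survival can be read only against outside figures, where the absolute level is what counts.

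**Working it through.** **1. The passages side by side**

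| Place | Duty after PD and the 4-week visit | Gives a dated alive status? |
|---|---|---|
| 6.2 | Follow until death or release | No interval, form or status item |
| 10.3 and Appendix III Follow-up Report | None, except toxicities and second malignancies | No |
| 5.0 flowsheet, 3-month column | Only without confirmed PD, or with ongoing toxicities | No |
| Death Report | All patients, once the death is known | Deaths only |
| 4.1.12, 10.1, opening of Appendix III | General availability or best effort | No interval or status item |
| Appendix III death note | Investigate deaths in an unspecified period | No |

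**2. Size (illustrative)**

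The plan states no survival figure for this regimen, so there is none to reproduce.

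Inputs from the plan:
- n = 50 (12.3).
- Accrual of 12.5 months, from 50 / 4 at the slower stated rate of 4 per month (12.3).
- Minimum follow-up of 6 months as the short case. Section 12.3 gives this for response assessment, not for survival. A follow-up of 24 months is the long case.
- Last scheduled contact at PD + 1 month (10.3).

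Assumptions:
- Exponential time to PD and exponential survival after PD, with medians of 6 + 6, 8 + 10 or 10 + 14 months.
- A fraction r of deaths after PD + 1 month is reported.
- All other patients are censored at the earlier of PD + 1 month and the cut-off.

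True 12-month survival, with a = ln 2 / (median to PD) and b = ln 2 / (median after PD), is

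S(12) = [a·exp(-12b) - b·exp(-12a)] / (a - b), or (1 + 12a)·exp(-12a) when a = b.

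- 6 + 6: 12a = 1.386, so S = 2.386 × 0.25 = 0.597.
- 8 + 10: S = 0.762.
- 10 + 14: S = 0.844.

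Mean Kaplan-Meier 12-month survival over 20,000 simulated trials per cell, with the error against full capture in brackets:

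| Follow-up | Medians | r = 1 | r = 0.9 | r = 0.75 | r = 0.5 |
|---|---|---|---|---|---|
| 6 months | 6 + 6 | 0.508 (-0.09) | 0.530 (-0.07) | 0.567 (-0.03) | 0.642 (+0.05) |
| 6 months | 8 + 10 | 0.694 (-0.07) | 0.712 (-0.05) | 0.742 (-0.02) | 0.797 (+0.03) |
| 6 months | 10 + 14 | 0.797 (-0.05) | 0.811 (-0.03) | 0.833 (-0.01) | 0.872 (+0.03) |
| 24 months | 6 + 6 | 0.585 (-0.01) | 0.600 (0.00) | 0.626 (+0.03) | 0.681 (+0.08) |
| 24 months | 8 + 10 | 0.744 (-0.02) | 0.756 (-0.01) | 0.777 (+0.015) | 0.818 (+0.06) |
| 24 months | 10 + 14 | 0.826 (-0.02) | 0.836 (-0.01) | 0.852 (+0.01) | 0.883 (+0.04) |

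The sampling standard deviation of the fully captured estimate is 0.079, 0.069 and 0.058 at 6 months and 0.069, 0.060 and 0.051 at 24 months, in the same order of medians.

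**3. Patients affected**

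The share alive at the 6-month cut-off with no scheduled contact is 0.30, 0.36 and 0.36. That is 50 × 0.30 = 15 to 50 × 0.36 = 18 patients.

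**4. Patients who stay on drug after CNS-only progression (10.2)**

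These patients remain in contact while on drug. If 30% of those who progress do so, the 6-month errors shrink to between -0.057 and +0.029. The share without contact falls to 0.21 to 0.25, or about 10 to 13 patients.

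**5. Effect of a vital-status sweep at cut-off** (6 months, 4,000 trials per cell)

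A complete sweep gives an error of 0.000 in all three scenarios. A sweep reaching 90% of patients, with r = 1 or 0.5 among the rest, leaves errors from -0.007 to +0.003.

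**The case against.** The passages can be read together: 10.3 limits scheduled visits and forms, while 6.2 keeps the patient on study, so the coordinating group could ask for vital status at any time. Late toxicities have no end date, and Section 9.1 keeps unexpected related serious events reportable indefinitely, so some contact after PD is presupposed. The death note makes investigators look into deaths. On that reading, losing half of later deaths would be a breach of the protocol rather than its design. The largest downward error needs a short follow-up that the plan never assigns to survival, and an analyst who censors early without querying sites. Every survival input is assumed, and so is the 12-month summary. The sentence in 12.2 on descriptive comparison with published data sits among text on response and toxicity and does not name survival. The case report forms are not in the documents.

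Much of this stands. The data may be recoverable, the magnitudes are illustrations, and no test or decision rests on survival. But none of these provisions sets an interval or asks for a dated alive status. The period in the death note is undefined. A status request at cut-off is possible but is not written down. A site could follow 10.3 to the letter and leave the survivors' dates blank.

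**Conclusion.** The concern holds. Section 6.2 conflicts with 10.3, Appendix III and the flowsheet in the current text, and the working schedule provides no alive date after progression for a named secondary endpoint. Under the stated assumptions the error in 12-month survival lies between -0.09 and +0.05 with 6 months' minimum follow-up, and between -0.02 and +0.08 with 24 months. Most of these errors are below one sampling standard deviation at n = 50, and the effect is small if death reporting is near complete and follow-up is long. The sign cannot be known in advance. The primary intracranial response rate and the sample size are not affected. This should be corrected, but it does not threaten the trial's main conclusion.

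**What to change.** - Reconcile 10.3, the Appendix III Follow-up Report and the flowsheet with 6.2, so that sites see one rule for patients who have progressed or relapsed.
- Require one vital-status check of every patient, by telephone or chart, at the overall-survival data cut-off. Record the date of death or the date last known alive.
- In Section 12, define overall survival with its time origin and cut-off, and state that patients not known to have died are censored at the date last known alive.
- Status checks every 3 months after progression are optional.

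The cost is one status check for each of at most 50 patients, one line each in 10.3 and Appendix III with the matching flowsheet entry, and a short definition in Section 12. It adds no visits or scans.
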